6.0 STUDY ASSESSMENTS

Table 1 summarizes the schedule for study visits and procedures performed at each study visit.

6.1 Prescreening, Screening, and Study Procedures

6.1.1 Prescreening Procedures

Subjects may be asked to sign a Prescreening Consent prior to undergoing a single nasopharyngeal swab (one nostril) for rapid influenza A testing. Subjects will be given a full explanation of the nature of the study and provide full written informed consent before any study-specific assessments or procedures are performed. Note: subjects that tested positive for influenza A within 48 hours prior to screening do not need to be retested.

6.1.2 Screening Procedures

Subjects will be given a full explanation of the nature of the study, provide full written informed consent before any study-specific assessments or procedures are performed, and undergo full screening procedures. Subjects will be assessed for inclusion and exclusion criteria, and those who fulfill all the inclusion and none of the exclusion criteria will be randomized into the study. A screen failure log must be maintained by the Investigator for all entry criteria failures. Table 1 lists the procedures performed at screening. Screening and baseline assessments (ie, Day 1 evaluations and procedures) may be performed on the same day.

6.1.3 Study Procedures

On Day 1, eligibility of the subjects will be confirmed and assessments will be performed as described in Table 1.

All results from the screening procedure needed to evaluate eligibility, including any local clinical laboratory results, must be available prior to randomization on Day 1. All clinical assessments required for the determination of subject eligibility will be performed by the local clinical laboratory, thereby precluding the need to wait for central laboratory data. Any abnormal assessment at the screening visit will be assessed according to its clinical relevance, and if found relevant, the subject will not be included in the study.

Once a subject has satisfied entry criteria, he/she will be assigned a unique identifier. The site's unblinded pharmacist or properly trained designee will access the Interactive Web Response System (IWRS) to obtain the study treatment. Randomization will be stratified by presence or absence of PPV at baseline to ensure balance between the treatment arms. Subjects will be considered randomized when the pharmacist or designee obtains the subject number and treatment assignment from the IWRS.

Subjects may not be randomized into this study more than once. Subjects who have participated in any previous study of VIS410 may not be randomized to this study. Subjects will be

monitored daily while in the hospital up to Day 14 (\pm 3 days) with an additional visit on Day 28 (\pm 3 days) and the last follow-up visit on Day 56 (\pm 7 days). In order to provide some flexibility for the subjects regarding the site visits and to maintain the integrity of the study design, a time window is permitted for the follow-up visits in case of time conflict or unforeseen circumstances. Note: subjects discharged from the hospital prior to Day 14 will attend the applicable outpatient follow-up visit(s) (eg, Day 3, Day 5, Day 7, Day 14).

6.1.4 **Unscheduled Visits**

Unscheduled visits can be planned at the discretion of the Investigator to obtain additional information to ensure the safety of the subject.

Unscheduled visits may be planned to assess, confirm, and follow up on out-of-range clinical laboratory test, vital sign, or ECG values that determine a subject's eligibility. Findings made during unscheduled visits should be recorded in the EDC system and the source documents.

Subjects will be instructed to contact the trial center if they exhibit worsening of symptoms or a new episode of influenza-like illness, so that they may be monitored and asked to return to the site for additional assessments (safety, nasopharyngeal swabbing) at the Investigator's discretion.

6.1.5 **Early Withdrawal Procedures**

Subjects should be encouraged to complete all study assessments. However, subjects who terminate the study before completion of the scheduled study procedures for any reason (AE, withdrawal of consent, etc.) should be encouraged to complete the early termination assessments (ie, identical to end of therapy [ET] assessments), including safety, prior to withdrawal, if possible.

6.1.6 **Treatment of VIS410 Overdose**

Given the absence of previous instances of VIS410 overdosing, clinicians have no specific treatment for the treatment of VIS410 overdose. However, high doses (ie, up to 4600 mg) have been evaluated in clinical study without any incidents of significant toxicity. In the event of VIS410 overdose, treatment administered to the subject(s) should be symptomatic and supportive.

Any overdose in this clinical study, with or without associated AEs, must be reported to the contract research organization (CRO) according to the procedures for SAE reporting as outlined in Section 9.7.1 and Section 9.7.2. All reports of overdose must be documented in the EDC. Any AEs associated with the overdose should be reported on relevant AE/SAE sections in the EDC.

6.2 **Pregnancy Safeguards**

Pregnancy will be determined by evaluation of β -human chorionic gonadotropin in serum or urine for all women of childbearing potential. Subjects who are pregnant or nursing will be

excluded from the study. During the course of the study drug administration period within the study, any nursing mother(s) or subject(s) with suspected or confirmed pregnancy will be discontinued from study drug therapy but will be encouraged to undergo follow-up for safety monitoring for themselves (ie, the pregnant female) and the baby.

All women of childbearing potential and all male subjects must practice effective contraception from screening until 60 days post-VIS410/placebo infusion. For the purposes of this study, women who do not satisfy at least one of the following criteria listed below (ie, the criteria for defining non-childbearing potential) are considered to be physiologically capable of becoming pregnant and are, therefore, defined as women of childbearing potential.

The criteria for defining women as being of non-childbearing potential are:

- Post-menopausal: \geq 12 months of natural (spontaneous) amenorrhea, or
- Follicle stimulating hormone $>$ 40 mIU/mL as documented in their medical history, or
- Surgical bilateral oophorectomy with or without hysterectomy, or
- Hysterectomy, or
- Bilateral tubal ligation

Women of childbearing potential and all male subjects participating in heterosexual relations must be willing to practice effective contraception from screening until 60 days post-VIS410/placebo infusion. For the purposes of the study, highly effective contraception is defined as:

- Male vasectomy with negative semen analysis documentation at least 6 months prior to dosing.

OR

- Combination of an established form of hormonal contraception (oral, injected, or implanted) or an intrauterine device or intrauterine system or sponge

Plus one of the following:

- A physical barrier method of contraception with use of a spermicide, such as condom or occlusive cap (diaphragm or cervical/vault caps) with spermicidal foam/gel/film/cream suppository. The use of barrier contraceptives should always be supplemented with the use of a spermicide, unless not available in a country. OR
- Male vasectomy with negative semen analysis documentation less than 6 months prior to dosing. OR
- Complete abstinence can be considered an acceptable method of contraception at the discretion of the Investigator. Periodic abstinences (eg, calendar, ovulation, symptothermal, or post-ovulation methods) and withdrawal are NOT considered acceptable methods of contraception.

The combination of 2 barrier methods, periodic abstinence (eg, calendar, ovulation, symptothermal, or post-ovulation methods), and withdrawal are not considered acceptable methods of contraception.

Male subjects should not donate sperm for at least 60 days after receipt of study product.

Pregnancy reporting is described in Section 9.7.3.

6.3 Procedures for Sample and Data Collection

6.3.1 SpO₂ Oxygen Support

Baseline SpO₂ on room air to be documented, if available. Once randomized, SpO₂ will be measured using pulse oximetry 3 times per day (approximately every 8 hours) at approximately the same time each day until stable according to Table 1. Stable SpO₂ is defined as two consecutive SpO₂ values of > 92% on room air that are at least 8 hours apart.

6.3.2 Viral Load

A nasopharyngeal swab will be collected from each nostril as described in Table 1 and Laboratory Manual. These swabs will be sent to a central virology laboratory for processing into appropriate aliquots for virology and PK analysis. Further details on sample collection, processing, shipment, and storage will be described in the Laboratory Manual.

The Investigator may also perform additional tests in the local laboratory consistent with SOC for the illness being treated.

Note: Virology samples taken from all subjects may be infectious and will be classified as “diagnostic specimens” for dispatch purposes.

6.3.3 Time to Cessation of Ventilator Support

Start and stop time for mechanical ventilation will be documented in EDC.

6.3.4 Resumption of Normal Activities

Subjects will complete a visual analog scale (VAS) daily from Day 1 (baseline) until either the subject reports that all usual activities (prior to influenza onset) can be performed or Day 56, whichever comes first. The VAS scale ranges from 0 to 10, where 0 indicates subject is unable to perform usual activities at all, and 10 indicates subject is able to perform all usual activities fully)

6.3.5 Health Resource Utilization

The following parameters for health resource utilization will be documented on an ongoing basis during the study:

- Hospital admission and discharge date
- ICU admission and discharge date
- Rehospitalization and reason for rehospitalization up to the last follow-up visit (Day 56 ± 7 days)

6.3.6 Signs and Symptoms of Influenza

The Influenza Patient-Reported Outcome (FluPRO) Questionnaire (see 14.1) must be completed (ie, self-reported) by the subject at baseline (Day 1) and post-dose as defined in Table 1. Each subject will be evaluated at baseline to determine if subject is able to independently report his/her influenza signs and symptoms. Subjects who are not able to complete the baseline FluPRO Questionnaire are exempt from this assessment throughout the study. The subject's inability to self-report his/her symptoms of influenza at baseline should be documented in the EDC.

6.3.7 Serum Pharmacokinetics

Throughout the study, 5-mL venous blood samples will be collected for analysis of VIS410 in serum, according to the time points defined in Table 1. The exact date and time of blood sampling and of administration of the study drug must be recorded in the EDC system. Serum samples for determination of the concentration of VIS410 will be analyzed under the responsibility of the Sponsor. Further procedures for sample collection, shipment, processing, and storage will be described in the Laboratory Manual.

6.3.8 Viral Resistance

Samples for virologic and PK analysis will be collected as described in Table 1 and the Laboratory Manual. These samples will be sent to a central virology laboratory for processing into appropriate aliquots for virology and PK analysis, including resistance testing.

Further procedures for sample collection, processing, shipment, and storage will be described in the Laboratory Manual.

Note: Nasopharyngeal and tracheal samples taken from all subjects may be infectious and will be classified as “diagnostic specimens” for dispatch purposes.

6.3.9 Clinical Outcomes per Seven-Level Ordinal Scale

The ordinal scale outcomes will be measured daily from Day 1 (baseline) through Day 14 using the following seven-level hierarchical scale with the classifications presented from the worst clinical outcome to the best clinical outcome in descending order.

For each day, subjects will be classified by the worst clinical outcome for which they qualify. For example, a patient with both ventilation and oxygen on the hospital floor on Day 1 will be classified as a mechanical ventilation patient for Day 1.

- Death
- ICU stay with mechanical ventilation
- ICU stay without mechanical ventilation
- Non-ICU hospitalization with supplemental oxygen
- Non-ICU hospitalization without supplemental oxygen
- Discharge with partial resumption of normal activities
- Discharge with full resumption of normal activities

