5.2.1 Inclusion Criteria

Subjects meeting all of the following criteria are eligible to participate in this study:

1. Male and female subjects aged ≥ 18 years. For a country where the legal age of consent is >18 years old, the country requirements should be followed.
2. Test positive for influenza A by rapid antigen test or with another commercially available test on an adequate nasopharyngeal specimen in accordance with the manufacturer's instructions, or an acceptable local test including, PCR, FIA, or ELISA.
3. Onset of influenza symptoms no more than 5 days before VIS410/placebo infusion; symptoms may include cough, dyspnea, sore throat, fever, myalgias, headache, nasal symptoms (rhinorrhea, congestion), fatigue, diarrhea, anorexia, nausea, and vomiting.
4. Requirement for oxygen support including any positive pressure ventilation (PPV).
5. Women of childbearing potential must have a negative pregnancy test within 2 days prior to VIS410/placebo infusion.
6. Women should fulfill one of the following criteria:
 - a. Post-menopausal: either amenorrhea ≥ 12 months or follicle stimulating hormone > 40 mIU/mL as documented in their medical history
 - b. Surgically sterile; hysterectomy, bilateral oophorectomy, or tubal ligation
 - c. Women of childbearing potential participating in heterosexual relations must be willing to use adequate contraception from screening until 60 days post-VIS410/placebo infusion (see Section 6.2).
7. Non-vasectomized (or vasectomized less than 6 months prior to dosing) male subjects who have a female partner of childbearing potential must use an effective birth control method (see Section 6.2) when having heterosexual intercourse, from screening until 60 days post-VIS410/placebo infusion.
8. Subject is able and willing to comply with study procedures, as per protocol.
9. Subject, or a legally acceptable representative, is able to understand the purpose and risks of the study and willing to give voluntary written informed consent.

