10.2 Randomization and Blinding

An IWRS will be used to allocate the randomized treatments to subjects with stratification by presence or absence of positive pressure ventilation (PPV) at baseline. Pharmacists must obtain the status of the subject relative to PPV at baseline via query, and this data must be input into the IWRS prior to randomization. The randomized treatment assignment will be transferred electronically for integration with the clinical study data at the appropriate time.

PPV includes any respiratory assistance using a mechanical ventilation device and can be either invasive or noninvasive ventilation. Invasive PPV includes intubation with endotracheal tube with mechanical ventilation (most common) or tracheostomy with mechanical ventilation. Noninvasive PPV includes use of facemask, nasal plugs, or nasal mask with mechanical ventilation. The devices are named according to the type of mechanical ventilation given continuous positive airway pressure (CPAP) or bi-level positive airway pressure (BiPAP).

Randomization will be used to avoid bias in the assignment of subjects to treatment, to increase the likelihood that known and unknown subject attributes (eg, demographic and baseline characteristics) are evenly balanced across treatment arms.

The maintenance of the study blind is critical for an unbiased assessment of the safety and efficacy of the study drug. All study staff that evaluate subjects and render decisions regarding subject care will remain blinded to the study treatment each subject receives.

The designated study site pharmacist or designee will remain unblinded. Also, unblinded clinical research associates will handle study drug accountability.

The study will be conducted in a double-blind manner. The CRO, site study personnel, and Visterra personnel will not be aware of which treatment (VIS410 or placebo) the subjects have been given. Subjects will not be aware of which treatment they have been administered.

Subjects will be randomized 1:1:1 to receive VIS410 2000 mg, VIS410 4000 mg, or placebo over a 2-hour infusion with pretreatment regimen of PO or IV diphenhydramine 50 mg plus either ibuprofen 400 mg PO or acetylsalicylic acid 320-325 mg PO approximately 60 minutes before IV infusion of VIS410/placebo.

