### **9.1 Primary Efficacy Analysis – Day 7 Ordinal Scale Status**

The ordinal scale outcomes will be measured daily from Day 1 (Baseline) through Day 14 using the seven-level hierarchical scale with the classifications presented in the table below. The clinical outcomes therein are ordered from the worst clinical outcome to the best clinical outcome in descending order. For each day, subjects will be classified by the worst clinical

January 17, 2019

outcome for which they qualify. The number and percentage of subjects in each treatment group with each classification will be summarized for each day from Day 1 through Day 14, inclusive. For subjects who die prior to Day 7, the score of 7 will be carried forward through Day 14. If a subject is missing an ordinal scale value but is bracketed by the same values on immediately preceding and subsequent days, the value of the missing day will be imputed to be the same as the immediately preceding and subsequent days. If a subject is missing baseline ordinal scale values from Day 1, baseline values will be set to the Day 2 score. If subjects are missing Day 1 and Day 2, the baseline value will not be imputed. No other data will be imputed.

Clinical Outcome	Score
Death	7
ICU stay with mechanical ventilation	6
ICU stay without mechanical ventilation	5
Non-ICU hospitalization with supplemental oxygen	4
Non-ICU hospitalization without supplemental oxygen	3
Discharge with partial resumption of normal activities	2
Discharge with full resumption of normal activities	1

For use in overall summary statistical presentations, the ordinal categories will be assigned decreasing integer scores, with death a score of 7 and discharge with full resumption of normal activities a score of 1. Frequencies of ordinal scores at each visit will be generated and evaluated by proportional odds ratio analysis, as implemented by logistic regression, including a test of the proportional odds assumption and generation of common odds ratios. For this analysis, the reference response category will be 1= Discharge with full resumption of normal activities with the remaining response categories in numeric sequence to worst (7=Death). Additional exploratory analyses may be conducted to obtain a more complete understanding of the relationship of treatment to the ordinal response.

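### The seven-level scale names ventilation only within an ICU stay and gives no scoring rule for ventilation on the ward, so the same state can be scored 4 (or 3) or 6 on the primary endpoint

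*Protocol*

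**What the plan says.** SAP 9.1 gives the scores. The only level that mentions ventilation is "ICU stay with mechanical ventilation" (6). The ward levels are "Non-ICU hospitalization with supplemental oxygen" (4) and the same without oxygen (3). Protocol 3.1.1, 6.3.9 and Table 8 use the same level names.

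Protocol 6.3.9 sets the daily rule: "For each day, subjects will be classified by the worst clinical outcome for which they qualify". It then illustrates the rule with "a patient with both ventilation and oxygen on the hospital floor on Day 1", who is to be counted for that day under mechanical ventilation.

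Protocol 10.2 defines positive pressure ventilation (PPV), the stratification factor: "PPV includes any respiratory assistance using a mechanical ventilation device and can be either invasive or noninvasive ventilation". It adds that "Noninvasive PPV includes use of facemask, nasal plugs, or nasal mask with mechanical ventilation", and names CPAP and BiPAP. Inclusion criterion 4 admits subjects on any PPV and makes no reference to an ICU.

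SAP 9.1 repeats the level names and the worst-outcome rule but not the example, and it has no rule for ventilation outside an ICU. Its sensitivity analysis rescores only subjects held in the ICU for reasons other than severity. SAP 9.2.1 compares days at the more severe scale values, including time on ventilator. SAP 9.2.4 derives time to cessation of ventilator support from the ordinal scale. Start and stop times of mechanical ventilation (protocol 6.3.3) and ICU admission and discharge dates (protocol 6.3.5) are recorded separately.

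**The concern.** The scale joins two things, place of care and respiratory support, and names ventilation in only one place of care. The trial nevertheless enrolls and stratifies on PPV wherever it is given. A site with a subject on BiPAP on the ward has to choose between the literal level name and one reading of the protocol's own example, and the two answers are two levels apart.

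The primary Day 7 score is exposed, and so are the ordinal AUC and the post-enrollment worsening analysis. The ventilator endpoints have a more direct problem. If noninvasive support counts as ventilation, a subject who leaves the ICU still on BiPAP goes from 6 to 4 by label. That registers as ventilator cessation and a two-level improvement although the support has not changed.

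About 140 sites are planned for about 120 subjects (protocol synopsis), or 120/140 ≈ 0.9 subjects per site. Differences in interpretation between sites therefore act almost subject by subject and will not show up as a visible site effect.

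**Working it through.** The plan states no power, effect size or rate of ward ventilation, so there is no figure of its own to reproduce beyond 3 × 40 = 120. The check has three parts, using SAP scores (1 best, 7 worst).

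**1. Texts side by side, for a subject ventilated on the ward**

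| Source | Score |
|---|---|
| Level names, subject also on supplemental oxygen | 4 |
| Level names, no supplemental oxygen | 3 |
| 6.3.9 example, read as ventilation given on the floor | ventilation patient; the only such level is 6, whose name requires an ICU stay |
| 6.3.9 example, read as ventilation and floor oxygen at different times that day | silent on ward ventilation; back to 4 or 3 |
| SAP 9.1 | no rule |

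A second question runs through every row: does mechanical ventilation on the scale include the noninvasive support that 10.2 counts as PPV? Neither document says.

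**2. Size per subject**

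- One day: 6 − 4 = 2 points.
- Summed daily scores, if the state lasted throughout: 2 × 7 = 14 (Days 1–7) and 2 × 14 = 28 (Days 1–14).
- By the trapezoidal rule, which SAP 9.2.1 also names: 2 × 6 = 12 and 2 × 13 = 26.

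**3. Illustrated effect on the Day 7 comparison**

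The model is proportional odds, logit P(Y ≤ j) = α_j − β·arm, with common odds ratio exp(β); values above 1 mean worse scores in the arm coded 1. The assumed Day 7 counts per 40 subjects, levels 1 to 7, are 6/12/6/10/2/3/1. They are not from the documents. Let k be the number of ward-ventilated subjects.

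- Scenario A: two identical arms, with the k subjects scored 6 in one arm and 4 in the other. The mean score shifts by 2k/40.
- Scenario B: k placebo subjects are ward-ventilated and their k active counterparts are at level 3. The odds ratio is active against placebo, under each scoring rule.

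| k of 40 | A: odds ratio (mean shift) | B: scored 4 | B: scored 6 |
|---|---|---|---|
| 1 | 1.03 (0.05) | 0.97 | 0.94 |
| 2 | 1.07 (0.10) | 0.94 | 0.89 |
| 3 | 1.11 (0.15) | 0.91 | 0.84 |
| 4 | 1.14 (0.20) | 0.88 | 0.80 |

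No p-value in the table falls below 0.57. Scenario A is deliberately extreme, because it needs the scoring to differ wholly by arm.

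**The case against.** The strongest defense is that the level names form a complete grid: dead; in the ICU with or without ventilation; on the ward with or without oxygen; discharged with partial or full activity. That stands. A reader might infer that a ward-ventilated subject has no level at all, but by label every living ward inpatient is a 4 or a 3. The difficulty is a competing instruction, not a missing category.

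The example also has a harmless reading. It illustrates the worst-outcome rule, so it may describe a patient ventilated at one time and on floor oxygen at another on the same day. It cannot be taken as proof that the protocol places ventilation on the floor. The harmless reading leaves ward ventilation unaddressed rather than settled, and the other reading remains available to sites.

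The five-level scale in SAP 9.2.1 is unambiguous by label, since any ward inpatient is a 2. The ambiguity reaches it only if it is built by collapsing recorded seven-level scores, in which case a recorded 6 would become a 4. The SAP does not say how it is built.

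The 10.2 definition serves stratification, and the scale never uses the term PPV. The SAP lists PPV and endotracheal intubation as separate subgroups. This shows that the term needs defining, not that ward CPAP belongs in level 6. Nor does the example's absence from the SAP show that sites ignored it when scoring.

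Finally, blinding and stratification by PPV make systematic scoring differences between arms unlikely, and the study is declared exploratory and unpowered. Both points hold and limit the effect on the primary comparison.

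**Conclusion.** The point holds as a scoring ambiguity worth correcting. It does not threaten the trial's main comparison. A ward-ventilated subject is 4 (or 3) by label and 6 on one fair reading of the protocol's example, and the SAP does not choose. By label the subject is also counted as off the ventilator in two secondary analyses.

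The likely effect on the Day 7 odds ratio is small: 1.03 to 1.14 in place of 1.00 under the extreme arm-wise scenario with 1 to 4 of 40 subjects. This rests on an assumed outcome distribution and an assumed number of ward-ventilated subjects. If one supposed that 5–15% of subjects were affected, that would be 6 to 18 of 120, but nothing in the documents supports that or any other rate.

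A reader might also conclude that all ward PPV should be scored 6. The documents do not support that. It would rank ward CPAP above an ICU stay without ventilation (5) and so redefine the primary endpoint.

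Correction is still worthwhile because the trial's stated purpose is to choose endpoints for Phase 3, and an unsettled scale would carry forward.

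**What to change.** Before unblinding:

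1. Reconcile the level names, the 6.3.9 example and the 10.2 definition into one stated rule for scoring ventilation outside the ICU. Say whether noninvasive support counts. Use the same words in protocol 3.1.1, 6.3.9 and Table 8 and in SAP 9.1 and 9.2.1, and say how the five-level score is derived.
2. Check recorded scores against the ventilation start and stop times and ICU dates in the EDC. First confirm that those times include noninvasive support, because protocol 6.3.3 uses the same undefined term and the eCRF is not among the documents.
3. Derive ventilator days and time to cessation of ventilator support from those times rather than from the ordinal level.
4. Report the Day 7 analysis with ward ventilation scored the other way, alongside the sensitivity analysis already in SAP 9.1, instead of moving all ward PPV to level 6.

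The cost is aligned wording in both documents, a small derivation from data already collected, and one extra table.
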